## Table 3. Operational definitions of study variables in the selected databases

aa The data sources are unable to reliably ascertain severity of hepatic impairment and renal impairment.

bb The data sources may not be able to differentiate between active and latent TB.

<sup>z In GKV claims, outpatient diagnoses are reported quarterly.

Variable	Role	Operational definition
Compliance to recommendations for limitations of use with concomitant medications not compatible with tofacitinib		
Use of biologics approved to treat RA, PsA, or UC while taking tofacitinib cc	Outcome: Concomitant medications not compatible with tofacitinib	Defined as ≥1 overlapping days' supply of a tofacitinib prescription dispensing and a prescription dispensing for a biologic approved to treat RA, PsA, or UC (as identified by ATC code[s]) during the follow-up period.
		Note: Concomitancy with a biologic can occur even if the contraindicated medication is dispensed prior to the index tofacitinib dispensing, provided that there is $\geq 1$ overlapping days' supply with a tofacitinib prescription dispensing during the follow-up period.
		Note: This variable will be presented overall and by patients with and without $\geq 2$ tofacitinib prescription dispensings dd during the follow-up period (where the second prescription is dispensed within 15 days of the last day of the days' supply [or the equivalent] of the first prescription).
		Duration of tofacitinib therapy defined in Section 9.3.3.
		Complete list of biologics in ANNEX 6. LIST OF ATC CODES FOR MEDICATIONS OF INTEREST TO AVOID WHILE TAKING TOFACITINIB.

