  - The proportion of patients with evidence of ≥1 malignancy risk factors *prior to* initiation of tofacitinib and no prior use of an alternative therapy (i.e., biologic), reported overall and by approved indication;
  - The proportion of patients who discontinue tofacitinib after developing ≥1 malignancy risk factor while taking tofacitinib; and
  - The proportion of patients who continue taking tofacitinib after developing ≥1 malignancy risk factor while taking tofacitinib;

- Contraindicated use, as measured by:e
  - A patient *initiating* tofacitinib therapy if they have severe hepatic impairment;i
  - A woman *initiating* tofacitinib therapy if she is pregnant;
  - A patient *initiating* tofacitinib therapy if they have or have had TB in the prior 2 months;
  - A patient initiating tofacitinib therapy if they have or have had a serious and/or opportunistic infection in the prior 2 months; and
  - A woman *receiving* tofacitinib therapy during her pregnancy;
- Use with concomitant medications not compatible with tofacitinib, as measured by:
  - The proportion of patients receiving biologics and/or potent immunosuppressants *while taking* tofacitinib; and
  - The proportion of patients receiving a live vaccination *while taking* tofacitinib;j

The secondary outcomes of interest will be:

- Tofacitinib prescribing patterns over time;e,f and
- Changes in the prescribing patterns (utilisation) of tofacitinib following the updated recommendations and limitations for use implemented after the 2019 Article 20 referral and the 2021 signal evaluation procedure, specifically:
  - Use in patients with VTE risk factors, as measured by:e,f
    - The proportion of patients with evidence of ≥1 VTE risk factors *prior to* initiation of tofacitinib, reported overall and by approved indication and stratified by VTE Reporting Periodk

<sup>i The data sources are unable to reliably ascertain severity of hepatic impairment; thus, this sub-outcome may be overestimated.

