### Table 3. Operational definitions of study variables in the selected databases

<sup>cc Biologics that are dispensed or administered primarily through hospital channels may not captured (completely) in the data sources.

<sup>dd Patients with  $\geq 2$  dispensings of tofacitinib are more likely to have taken tofacitinib for the full days' supply of the prescription as opposed to patients with only 1 dispensing of tofacitinib.

Variable	Role	Operational definition
Use of selected potent immunosuppressants while taking tofacitinib	Outcome: Concomitant medications not compatible with tofacitinib	Defined as ≥1 overlapping days' supply of a tofacitinib prescription dispensing and a prescription dispensing for the selected potent immunosuppressants azathioprine, 6-mercaptopurine, cyclosporine, or tacrolimus (as identified by ATC code[s]) during the follow-up period.
		Note: Concomitancy with a selected potent immunosuppressant can occur even if the contraindicated medication is dispensed prior to the index tofacitinib dispensing, provided that there is $\geq 1$ overlapping days' supply with a tofacitinib prescription dispensing during the follow-up period.
		Note: This variable will be presented overall and by patients with and without ≥2 tofacitinib prescription dispensings dd during the follow-up period (where the second prescription is dispensed within 15 days of the last day of the days' supply [or the equivalent] of the first prescription).
		Duration of tofacitinib therapy defined in Section 9.3.3.
		Complete list of selected potent immunosuppressants in ANNEX 6. LIST OF ATC CODES FOR MEDICATIONS OF INTEREST TO AVOID WHILE TAKING TOFACITINIB.

 Table 3.
 Operational definitions of study variables in the selected databases
X7	D.1.	
variable	Kole	Operational definition
Receipt of a live vaccination while taking tofacitinib ee	Outcome: Concomitant medications not compatible with tofacitinib	Defined as $\geq 1$ procedure code and/or $\geq 1$ prescription dispensing (as identified by ATC code[s]) for a live vaccination (as available) while receiving tofacitinib therapy in the follow-up period.

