#### 9.7.1.2.2.1.6. Use with concomitant medications not compatible with tofacitinib

The proportion of tofacitinib patients with concomitant use of medications not compatible with tofacitinib will be reported overall and by patients with and without  $\geq 2$  tofacitinib prescription dispensings.ss Additionally, the number of overlapping days' supply of the biologic or selected potent immunosuppressant with the tofacitinib prescription dispensing will be described continuously and categorically (e.g., 1-7 days, 8-14 days, 15-21 days, 22-30 days,  $\geq 31$  days; final cut-offs to be determined after examining the distribution of the data).

9.7.1.3. Secondary Objectives 1 and 2: Describe prescribing patterns; and Describe changes in tofacitinib prescribing patterns (utilisation) following the updated recommendations and limitations for use implemented after the 2019 Article 20 referral and the 2021 signal evaluation procedurett,uu,vv,ww

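### One day of leftover supply from a drug dispensed only before tofacitinib started counts as incompatible use, so the headline proportion mixes switching with co-use

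*Protocol*

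**What the plan says.** The outcome belongs to primary objective 2. Section 9.3.1 lists it as "The proportion of patients receiving biologics and/or potent immunosuppressants" while taking tofacitinib. Table 3 places it under "Compliance to recommendations for limitations of use with concomitant medications not compatible with tofacitinib".

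For biologics, Table 3 reads: "Defined as ≥1 overlapping days' supply of a tofacitinib prescription dispensing and a prescription dispensing for a biologic" approved for one of the three indications, during follow-up. A note then says "Concomitancy with a biologic can occur even if the contraindicated medication is" dispensed "prior to the index tofacitinib dispensing, provided that there is" at least one overlapping day in follow-up. For azathioprine, 6-mercaptopurine, cyclosporine and tacrolimus the note is the same: "Concomitancy with a selected potent immunosuppressant can occur even if the contraindicated medication is" dispensed before index. Neither entry requires the other drug to be dispensed after index.

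Two features qualify the headline figure:

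- The outcome is shown overall and for patients with and without at least two tofacitinib dispensings. A footnote explains that a second dispensing makes it more likely that tofacitinib was actually taken.
- Section 9.7.1.2.2.1.6 adds that "the number of overlapping days' supply of the biologic or selected potent immunosuppressant with the tofacitinib prescription dispensing will be described continuously and categorically". Example bands run from 1-7 to 31 or more days, and the final cut-offs are chosen once the data have been seen.

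**The concern.** Dispensing data show supply, not intake. Section 9.9 accepts this: actual use cannot be determined, days' supply will be a proxy, and for newly acquired VTE risk factors it concedes that one cannot tell whether a prescription already filled was stopped. Section 9.9 does not apply the same reasoning to a biologic stopped part-way through its supply when tofacitinib begins.

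Such a patient overlaps on paper without necessarily combining the drugs. The reverse can happen at the other end, when a biologic is dispensed before the calculated tofacitinib supply has run out. Both are counted as departures from a limitation of use.

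A further tension is that the same Annex 6 biologic list defines alternative therapy. In the age, CV and malignancy outcomes, the adverse finding is having no biologic in the 12 months before index. A recent switcher can therefore look favourable there and adverse here on the strength of one dispensing record. What is at stake is whether this proportion can be read as prescriber compliance.

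**Working it through.** **1. The rule applied to one patient.** A biologic with 28 days' supply is dispensed on day 0, and tofacitinib is first dispensed on day 20. No biologic follows. Overlap = 28 − 20 = 8 days, so the patient is flagged. A patient who keeps receiving both drugs is flagged by the same rule. Nothing in the reported outcome tells the two apart by when the other drug was dispensed.

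**2. The plan's own figure.** The protocol gives no expected value for this outcome. Its general precision target (Section 9.5) is 0.50 × 0.50 × 1.96² / 0.10² = 96.04, rounded up to 97. This reproduces. It is used below only as a yardstick: a 10-point margin of error.

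**3. How many pure switchers would be flagged.** The protocol states neither the supply length of the other drug (D) nor the timing of switches, so both are assumed. Tofacitinib starts on a day t spread evenly over 0 to G − 1 after the last dispensing of the other drug, which is not dispensed again. Overlap = max(0, D − t), so the share flagged = min(D, G)/G.

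| D (days) | G = 28 | G = 56 | G = 90 | G = 180 |
|---|---|---|---|---|
| 14 | 50% | 25% | 16% | 8% |
| 28 | 100% | 50% | 31% | 16% |
| 56 | 100% | 100% | 62% | 31% |
| 84 | 100% | 100% | 93% | 47% |

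**4. Whether the overlap bands separate the two groups.** With D = 28 the overlap cannot exceed 28 days, so every such switcher falls in a band of 30 days or less and is visible as short overlap. For D above 30, the share of pure switchers in the example top band of 31 or more days is min(D − 30, G)/G.

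| D (days) | G = 28 | G = 56 | G = 90 | G = 180 |
|---|---|---|---|---|
| 56 | 93% | 46% | 29% | 14% |
| 84 | 100% | 96% | 60% | 30% |

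With longer supplies, leftover supply therefore reaches the same band as sustained co-use.

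**5. Whether the dispensing split separates them.** It is defined on tofacitinib alone. A patient who switches in and stays on tofacitinib has two or more dispensings, as does a true co-user.

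**6. Scale, as illustration only.** Suppose true co-use is 2%, a share s of the remaining patients are pure switchers, and a fraction f of those is flagged. Observed proportion = 0.02 + 0.98 × s × f.

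- s = 0.3, f = 0.16: 6.7%
- s = 0.5, f = 0.31: 17.2%
- s = 0.7, f = 1.0: 70.6%

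The excess over 2% is 4.7, 15.2 and 68.6 points, against the 10-point yardstick. Every input here is assumed. The result shows that the admixture could be small or dominant, not what it is.

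**The case against.** The strongest reply is that a sensitive definition suits a risk-minimisation outcome, and that reporting overlap length lets readers judge how much rests on a few days. This stands in part: the bands are informative for supplies of 30 days or less, and the long supplies in the tables are assumptions. It is a reason to keep the one-day rule. It is no reason to leave the two sources of overlap unseparated, particularly when the cut-offs are chosen after looking at the data.

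A second reply is that Section 9.3.2 calls the algorithms and codes preliminary, and that days' supply is left to the SAP. That covers code lists and the proxy. The one-day threshold and the counting of pre-index dispensings are stated outright in Table 3.

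A third is that biologics given through hospital channels are incompletely captured (Table 3 footnote) and, for Sweden, will be missed (Section 9.9). This is correct and lowers the outcome. It leaves the net direction of error unknown; it does not remove the mixture.

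Several stronger inferences are tempting and unsupported:

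- **That the outcome measures switching instead of co-use.** It captures both. Switches made after supply has run out are not counted at all.
- **That some definite share of initiators, say a third or a half, would be wrongly flagged.** Any such figure only restates an assumed share of direct switchers.
- **That the outcome would rise mechanically across the reporting periods.** The secondary outcomes do not include concomitant medication, and Section 9.7.1.2.2.1.6 does not stratify it by reporting period.
- **That a 90-day grace period in Hungary inflates it.** Section 9.3.3 gives 90 days as an example for duration of therapy, whereas this outcome is defined on days' supply.
- **That flagged patients are largely those rated appropriate elsewhere.** The alternative-therapy outcomes apply to particular subgroups and mostly look back 12 months, so many biologic-experienced patients would not be flagged here. The tension does not reach the immunosuppressants.

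**Conclusion.** The point holds in a limited form. Table 3 lets one day of residual supply, even from a dispensing made only before index, count as use while taking tofacitinib. The headline proportion therefore combines leftover supply at a switch with true co-use in an unknown ratio. The two planned breakdowns only partly reveal this, and neither separates dispensings before index from those after it.

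The size cannot be obtained from the protocol. The range of about 8% to 100% of pure switchers rests on assumed supplies of 14 to 84 days and an even spread of switch times over 28 to 180 days. It comes before any loss from incomplete capture of hospital biologics. The study is descriptive and no comparison depends on this outcome, so this is a cheap improvement and not a must-fix.

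**What to change.** Keep the overlap of at least one day and label it as the sensitive, upper-bound measure. In Section 9.7.1.2.2.1.6, report the patients it flags in three rows, separately for biologics and for the selected immunosuppressants:

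- **(a)** overlap arising only from dispensings of the other drug before index (possible switch in);
- **(b)** the other drug dispensed after index, with a further tofacitinib dispensing afterwards (co-use more likely);
- **(c)** the other drug dispensed after the last tofacitinib dispensing (possible switch out).

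State where a same-day dispensing goes, and place a patient who meets both (b) and (c) in (b), so that the rows add up to the headline. Fix the overlap bands before the data are examined. Add switching to Section 9.9 as a source of misclassification for this outcome.

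The dates needed are those already used to compute overlap. The cost is extra table rows with smaller cells. Row (a) may still contain some true co-use, so it should be shown and not discarded. No wash-out or other clinical rule is proposed.

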### Table 3. Operational definitions of study variables in the selected databases

<sup>cc Biologics that are dispensed or administered primarily through hospital channels may not captured (completely) in the data sources.

<sup>dd Patients with  $\geq 2$  dispensings of tofacitinib are more likely to have taken tofacitinib for the full days' supply of the prescription as opposed to patients with only 1 dispensing of tofacitinib.

Variable	Role	Operational definition
Use of selected potent immunosuppressants while taking tofacitinib	Outcome: Concomitant medications not compatible with tofacitinib	Defined as ≥1 overlapping days' supply of a tofacitinib prescription dispensing and a prescription dispensing for the selected potent immunosuppressants azathioprine, 6-mercaptopurine, cyclosporine, or tacrolimus (as identified by ATC code[s]) during the follow-up period.
		Note: Concomitancy with a selected potent immunosuppressant can occur even if the contraindicated medication is dispensed prior to the index tofacitinib dispensing, provided that there is $\geq 1$ overlapping days' supply with a tofacitinib prescription dispensing during the follow-up period.
		Note: This variable will be presented overall and by patients with and without ≥2 tofacitinib prescription dispensings dd during the follow-up period (where the second prescription is dispensed within 15 days of the last day of the days' supply [or the equivalent] of the first prescription).
		Duration of tofacitinib therapy defined in Section 9.3.3.
		Complete list of selected potent immunosuppressants in ANNEX 6. LIST OF ATC CODES FOR MEDICATIONS OF INTEREST TO AVOID WHILE TAKING TOFACITINIB.

 Table 3.
 Operational definitions of study variables in the selected databases
X7	D.1.	
variable	Kole	Operational definition
Receipt of a live vaccination while taking tofacitinib ee	Outcome: Concomitant medications not compatible with tofacitinib	Defined as $\geq 1$ procedure code and/or $\geq 1$ prescription dispensing (as identified by ATC code[s]) for a live vaccination (as available) while receiving tofacitinib therapy in the follow-up period.
		Note: This variable will be presented overall and by patients with and without ≥2 tofacitinib prescription dispensings dd during the follow-up period (where the second prescription is dispensed within 15 days of the last day of the days' supply [or the equivalent] of the first prescription)
		Duration of tofacitinib therapy defined in Section 9.3.3.
		Complete list of vaccinations in ANNEX 7. LIST OF ATC CODES FOR COMEDICATIONS OF INTEREST.
Secondary Objectives 1 and utilisation of tofacitinib foll Article 20 referral and the 2	2: Describe prescribing patterns over owing the updated recommendations 2021 signal evaluation procedure ff,gg	time; and Describe changes in the and limitations for use after the 2019
In patients with VTE risk	factors (will be assessed separately in	n VTE Reporting Periods 1, 2, and 3 hh )
Initiating tofacitinib with $\geq 1$ VTE risk factor	Outcome: Changes in the utilisation of tofacitinib—VTE risk factors	See 'Primary Objective 2: Prescribers' adherence to the tofacitinib aRMMs – Compliance to recommendations to
Number of VTE risk factors identified prior to	Outcome: Changes in the utilisation of tofacitinib —VTE risk factors	limitations for use in patients with VTE risk factors ' for operational definitions.

 Table 3.
 Operational definitions of study variables in the selected databases

<sup>ee This study sub-outcome will not be assessed in Sweden because most vaccinations are not done in specialist care and therefore are not captured in the NPR, nor are vaccines prescribed and purchased by the patients in the pharmacies and therefore are not be captured in the PDR. Vaccination data are also unavailable in the PHARMO Database Network. In GKV claims, it is not possible to differentiate between live and non-live vaccines.

<sup>ff The study outcomes that contain an ADD component will *not* be assessed in Hungary or the Netherlands. The Hungarian administrative claims database is unable to estimate ADD, either directly or by proxy, due to how tofacitinib is captured in the database. In the high-budget impact medication dataset of the PHARMO Database Network, neither ADD nor the number of pills per prescription is captured.

<sup>gg In GKV claims, outpatient diagnoses are reported quarterly.

<sup>hh Hungary will not have a VTE Reporting Period 1. Hungary will also not have a VTE Reporting Period 2 for PsA and UC.

Variable	Role	Operational definition
Number of UC patients with: $\geq 1$ VTE risk factor; no prior alternative therapy (i.e., biologic); and an ADD >10 mg in Weeks 16-23, Weeks 24- 31, Weeks 32-39, and Weeks 40-47 of follow-up t	Outcome: Changes in the utilisation of tofacitinib —VTE risk factors	
Discontinuation of tofacitinib after developing ≥1 VTE risk factors while taking tofacitinib	Outcome: Changes in the utilisation of tofacitinib —VTE risk factors	
Continuation of tofacitinib after developing ≥1 VTE risk factors while taking tofacitinib	Outcome: Changes in the utilisation of tofacitinib —VTE risk factors	
Use in the elderly (patients 2, and 3, hh and CV and Ma	65 years and older) (will be assessed lignancy Reporting Periods 1, 2, and	l separately in VTE Reporting Periods 1, l 3 ii )
Initiating tofacitinib with no prior use of an alternative therapy (i.e., biologic) among patients 65 years of age and older	Outcome: Changes in prescribing patterns—Age 65 years and older	See 'Primary Objective 2: Prescribers' adherence to the tofacitinib aRMMs – Compliance to recommendations to limitations for use in patients aged 65 years and older' for operational
Discontinuation of tofacitinib for patients who turn 65 years old while receiving tofacitinib	Outcome: Changes in prescribing patterns—Age 65 years and older	definitions.
Failure to discontinue tofacitinib for patients who turn 65 years old while receiving tofacitinib	Outcome: Changes in prescribing patterns—Age 65 years and older	
Appropriate continuation of tofacitinib for patients who turn 65 years old while receiving tofacitinib	Outcome: Changes in prescribing patterns—Age 65 years and older	

 Table 3.
 Operational definitions of study variables in the selected databases

<sup>ii Hungary will not have a CV and Malignancy Reporting Period 1 or a CV and Malignancy Reporting Period 2 for PsA and UC.

Variable	Role	Operational definition
In patients with CV risk fa 1, 2, and 3 ii and stratified b	ctors (will be assessed separately in by sex as outlined in Section 9.7.1.3.3	CV and Malignancy Reporting Periods [Use in patients with CV risk factors])
Initiating tofacitinib with $\geq 1 \text{ CV}$ risk factor	Outcome: Changes in the utilisation of tofacitinib —CV risk factors	See 'Primary Objective 2: Prescribers' adherence to the tofacitinib aRMMs – Compliance to recommendations to limitations for use in patients with CV
Initiating tofacitinib with $\geq 1$ CV risk factor and no prior use of an alternative therapy (i.e., biologic)	Outcome: Changes in the utilisation of tofacitinib —CV risk factors	risk factors ' for operational definitions.
Discontinuation of tofacitinib after developing ≥1 CV risk factors while taking tofacitinib	Outcome: Changes in the utilisation of tofacitinib —CV risk factors	
Continuation of tofacitinib after developing ≥1 CV risk factors while taking tofacitinib	Outcome: Changes in the utilisation of tofacitinib —CV risk factors	
In patients with malignance Periods 1, 2, and 3 ii )	y risk factors (will be assessed separ	ately in CV and Malignancy Reporting
Initiating tofacitinib with ≥1 malignancy risk factor	Outcome: Changes in the utilisation of tofacitinib — Malignancy risk factors	See 'Primary Objective 2: Prescribers' adherence to the tofacitinib aRMMs – Compliance to recommendations to
Initiating tofacitinib with ≥1 malignancy risk factor and no prior use of an alternative therapy (i.e., biologic)	Outcome: Changes in the utilisation of tofacitinib — Malignancy risk factors	limitations for use in patients with malignancy risk factors ' for operational definitions.
Discontinuation of tofacitinib after developing ≥1 malignancy risk factors while taking tofacitinib	Outcome: Changes in the utilisation of tofacitinib — Malignancy risk factors	
Continuation of tofacitinib after developing ≥1 malignancy risk factors while taking tofacitinib	Outcome: Changes in the utilisation of tofacitinib — Malignancy risk factors	

